9.2 Unscheduled Visit

At any time during the study, the subject may have an additional study visit/phone call if the investigator or the subject feels it is necessary. All information, including reason for visit/phone call, AEs, and any procedures performed should be collected in the source documents and recorded in the appropriate section of the eCRF.

9.3 Safety Assessments

Safety will be assessed by the nature, frequency, and severity of treatment-emergent spontaneously reported AEs, dropouts due to AEs, overall dropout rates, and changes from baseline in vital signs, physical and neurologic exams, clinical laboratory evaluations, 12-lead ECGs, and Columbia-Suicide Severity Rating Scale (C-SSRS).

Study subjects will receive the following Hypersensitivity information on a laminated card to carry with them:

- Rash may occur and may progress to Drug Reaction with Eosinophilia and Systemic Symptoms (DRESS).
- Rash or other signs or symptoms of hypersensitivity (e.g., fever, lymphadenopathy, and swelling) may herald a serious medical event and that the patient should report any such occurrence to the investigative site immediately.
- Instructions on whom and where to call in the event a symptom arises and information that can be provided to an emergency room in the event the subject cannot reach the investigator site.
- Reminder to check skin daily for evidence of rash for the first four months of therapy

If a subject reports a rash by telephone, an unscheduled visit should be performed promptly. Any patient with a rash or manifestation of hypersensitivity reaction such as lymphadenopathy, fever, facial swelling must be seen immediately at the study site. If it can definitely be determined that the rash or other symptoms are unrelated to study drug, then the subject can be maintained on YKP3809. If the cause of the rash or other symptoms cannot be definitely determined immediately, then YKP3809 must be discontinued immediately.

The initial physical/rash assessment for hypersensitivity reaction at the investigative site will include the following:

- Measure body temperature

9.4 Pharmacokinetic Evaluations

Time and date of each blood draw and dosing records (time/date/dose) of YKP3089 and AEDs prior to each blood draw will be recorded on the eCRF and other appropriate forms.

Plasma samples will be assayed for YKP3089 and AEDs at a specified bioanalytical laboratory using previously validated methods. Assay methodology will be detailed in separate assay protocols.

For subject taking phenytoin or phenobarbital

These samples will be obtained from subjects taking phenobarbital or phenytoin at any global sites.

At Visit 2, a single trough level of phenytoin or phenobarbital will be obtained. At Visits , 4, 5, 6, 7 and 8, two blood samples will be collected for the determination of phenobarbital or phenytoin plasma levels: For the subjects taking phenytoin or phenobarbital in the morning and coming into the visits in the morning, the first blood draw will be collected upon subjects' arrival to the study unit; the second blood draw should be collected within 30 minutes to 2 hours after the medication is taken. At Visits 8 and 9, two blood samples will be collected for YKP3089 depending on stability of dosing (stable dose all AEDs including YKP3089 for prior 2 weeks).

For subject taking concomitant AEDs other than phenytoin or phenobarbital

These samples will be obtained from subjects taking concomitant AEDs other than phenobarbital or phenytoin at US sites only.

At Visit 2, a single blood sample will be drawn to determine trough level if the subject is taking one of the followings, oxcarbazepine, topiramate, lamotrigine, lacosamide, clobazam, perampanel and levetiracetam. At Visit 8 and/or 9, two blood samples will be drawn from the same subjects to determine plasma levels of YKP3089, oxcarbazepine, topiramate, lamotrigine, lacosamide, clobazam, perampanel and levetiracetam. Collect at visit 8 and/ or 9 depending on stability of dosing (stable dose all AEDs including YKP3089 for prior 2 weeks). At Visit 8 and 9, for the subjects that are taking concomitant AEDs in the morning and coming into the visits in the morning, first blood draw will be collected upon subjects' arrival to the study unit; the second blood draw should be collected within 30 minutes to 2 hours after the medication is taken. For

patients that are taking concomitant AEDs in the afternoon and/or coming into the visits in the afternoon, the first blood draw will be collected upon subjects' arrival to the study unit; the second blood draw should be collected within 30 minutes to 2 hours after the first blood draw with timing of the dose, blood draws and strength of previous dose clearly documented.

The collection schedule is summarized in [Table 11](#) below.

Table 11. Blood Collection Schedule* for YKP3089 and AED Levels

Cohort →	Subjects taking Phenytoin or Phenobarbital	Subjects taking AEDs other than Phenytoin or Phenobarbital –US sites only
Blood collection for YKP3089 levels	Visits 8 and/or 9	Visits 8 and/or 9
Blood collection for phenytoin or phenobarbital levels	Visits 2*, 4, 5, 6, 7 and 8	Not Applicable
Blood collection for concomitant AEDs (other than phenytoin or phenobarbital) levels	None	Visits 2*, 8 and/or 9

* At Visit 2, one sample will be collected; at all other visits, two samples will be collected

Additional Samples

Additional blood samples may be drawn for levels of concomitant AEDs during the open label maintenance phase if the investigator believes that symptoms of toxicity may be related to concomitant AEDs.

10 SAFETY AND ADVERSE EVENTS

10.1 Definitions

10.1.1 *Adverse Events*

An adverse event (AE) is any symptom, sign, illness, or experience that develops or worsens in severity during the course of the study. Intercurrent illnesses or injuries should be regarded as AEs. Abnormal results of diagnostic procedures are considered to be AEs if the abnormality:

- Results in study withdrawal
- Is associated with an SAE
- Is associated with clinical signs or symptoms
- Leads to additional treatment or to further diagnostic tests
- Is considered by the investigator to be of clinical significance

10.1.2 *Serious Adverse Event*

AEs are classified as serious or non-serious. A *serious adverse event* is any AE that is:

- Fatal
- Life-threatening
- Requires or prolongs hospital stay
- Results in persistent or significant disability or incapacity
- A congenital anomaly or birth defect
- An important medical event

Important medical events are those that may not be immediately life threatening but are clearly of major clinical significance. They may jeopardize the subject and may require intervention to prevent one of the other serious outcomes noted above. For example, drug overdose or abuse, a seizure that did not result in inpatient hospitalization, or intensive treatment of bronchospasm in an emergency department would typically be considered serious.

10.1.3 *Suspected Adverse Reaction*

Suspected adverse reaction means any AEs for which there is a reasonable possibility that the drug cause the AE. For the purpose of investigational new drug (IND) safety reporting, “reasonable possibility” means there is evidence to suggest a causal relationship between the drug and AE. Suspected adverse reaction implies a lesser degree of certainty about causality than adverse reaction, which means any AE caused by a drug.

All AEs that do not meet any of the criteria for seriousness should be regarded as *non-serious AEs*.

10.1.4 *Adverse Event Reporting Period*

The study period during which AEs must be reported is normally defined as the period from the initiation of any study procedures (Visit 1) to the end of the study treatment follow-up. For this study, the AE reporting period is defined as 30 days following the last administration of study treatment for SAEs. For all other AEs, reporting period is defined as 14 days following the last administration of study treatment.

10.1.5 *Preexisting Condition*

A preexisting condition is one that is present at the start of the study. A preexisting condition should be recorded as an AE if the frequency, intensity, or the character of the condition worsens during the study period.

At Visit 1 any clinically significant abnormality should be recorded as a preexisting condition. At the end of the study, any new clinically significant findings/abnormalities that meet the definition of an AE must also be recorded and documented as an AE.

Post-study Adverse Events

All unresolved AEs should be followed by the investigator until the events are resolved, the subject is lost to follow-up, or the AE is otherwise explained. At the last scheduled visit, the investigator should instruct each subject to report any subsequent event(s) that the subject, or the subject's personal physician, believes might reasonably be related to participation in this study.

The investigator should notify the study Sponsor of any death or AE occurring at any time after a subject has discontinued or terminated study participation that may reasonably be related to this study. The Sponsor should also be notified if the investigator should become aware of the development of cancer or of a congenital anomaly in a subsequently conceived offspring of a subject who has participated in this study.

Abnormal Laboratory Values

A clinical laboratory abnormality should be documented as an AE if *any one of the following* conditions is met:

- The laboratory abnormality is not otherwise refuted by a repeat test to confirm the abnormality.
- The abnormality suggests a disease and/or organ toxicity.
- The abnormality is of a degree that requires active management (eg, change of dose, discontinuation of the drug, more frequent follow-up assessments, further diagnostic investigation).

Hospitalization, Prolonged Hospitalization, or Surgery

Any AE that results in hospitalization or prolonged hospitalization should be documented and reported as a serious AE unless specifically instructed otherwise in this protocol. Any condition responsible for surgery should be documented as an AE if the condition meets the criteria for an AE.

Neither the condition, hospitalization, prolonged hospitalization, nor surgery are reported as an AE in the following circumstances:

- Hospitalization or prolonged hospitalization for diagnostic or elective surgical procedures for a preexisting condition. Surgery should **not** be reported as an outcome of an AE if the purpose of the surgery was elective or diagnostic and the outcome was uneventful.
- Hospitalization or prolonged hospitalization required to allow efficacy measurement for the study.
- Hospitalization or prolonged hospitalization for therapy of the target disease of the study, unless it is a worsening or increase in frequency of hospital admissions as judged by the clinical investigator.
- An Emergency Room visit is not considered hospitalization.

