7.5 Birth Control Methods Allowable for Enrollment of Subjects

Sexually active female subjects of reproductive potential must practice an approved method of contraception during the entire study and for 30 days after the last dose of study medication. Hormonal contraceptives alone will not be considered an adequate method of contraception.

Women of childbearing/reproductive potential are defined as: Any female who has experienced menarche and does not meet the criteria for “Women Not of Childbearing Potential”. Women not of childbearing potential are defined as women who are postmenopausal or permanently sterilised (e.g. tubal occlusion, hysterectomy, bilateral salpingectomy).

Acceptable methods include:

- Hormonal contraception (for at least 3 months prior to Visit 1) in combination with a barrier method.
- Intrauterine device (placement at least 3 months prior to Screening visit)
- Diaphragm with spermicide
- Cervical cap
- Condoms with contraceptive gel/foam or cream
- Surgical sterilization (tubal ligation at least 6 months prior to screening or partner who has had vasectomy at least 6 months prior to screening)
- Postmenopausal (as defined by absent menses for at least 12 months)
- Abstinence; however, if the subject becomes sexually active, 1 of the above methods must be utilized.

There is no need for male subjects enrolled in YKP3089C021 study to use contraception with partners of childbearing potential during their participation in the study.

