9 STUDY PROCEDURES AND ASSESSMENTS

Visit windows of ± 2 days allowed for Visits 3 through 10.

Visit windows of ± 7 days allowed for all other open-label visits.

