Visit 15 represents the Follow-up Visit after discontinuation of study drug. This final visit will take place 14 days after the subject's last dose of YKP3089—at any time during the open-label treatment or after 12 months of open-label treatment if there is no additional treatment beyond that point.

As shown in [Table 1](#), the following assessments will be performed at Visit 15:

- Record vital signs
- Measure weight
- Conduct full neurologic examination
- Administer C-SSRS (Since Last Visit version)
- Serum pregnancy test (for female subjects of child-bearing potential)
- Draw blood for laboratory safety assessment
- Record concomitant medications
- Perform drug accountability if tapered
- Record AEs

No study drug will be dispensed.

9.1.16 *Open-Label Extension Beyond Year One*

Subjects who complete Visit 14 and will continue in the open-label treatment beyond year one will adhere to the following visit schedule. The investigator will schedule a return visit in 3 months. Subjects will have study visits every 3 months for a total of 4 visits per study year. The investigator will perform some or all of the following assessments depending up on the visits.

Perform the following every 3 months from Visit 14

- Record vital signs
- Conduct brief neurologic examination if required
- Administer C-SSRS (Since Last Visit version)
- Perform urine pregnancy test (for female subjects of childbearing potential)

- Record concomitant medications
- Perform drug accountability
- Record AEs
- Dispense open-label study drug bottles as instructed by IWRS

Perform the following every 6 months from Visit 14

- Measure weight
- Draw blood for laboratory safety assessment

Perform the following every 12 months from Visit 14

- Perform full physical exam
- Perform 12-lead ECG once
- Obtain urine for urinalysis

This pattern will continue at the discretion of the investigator until development is stopped by SK Life Science Inc, the product is approved for marketing, or anytime at the discretion of SK Life Science Inc.

After the first year of open-label treatment, the visits will be numbered sequentially beginning with Visit 16.

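### SAEs are reportable for 30 days after the last dose whatever their cause, but from day 15 no contact is scheduled and subjects are asked to report only events believed related

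*Protocol*

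**What the plan says.** **The duty.** Protocol section 10.1.4 states: "For this study, the AE reporting period is defined as 30 days following the last administration of study treatment for SAEs". The next sentence sets a shorter period for the rest: "For all other AEs, reporting period is defined as 14 days following the last administration of study treatment". Section 10.1.4 is silent on causality. Section 10.3.1 supplies that point: SAEs go to the sponsor's designee whether or not they are expected or thought related. Section 10.3 brings in a relatedness condition only for SAEs that occur after the study period.

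**The last contact.** Of Visit 15, section 9.1.15 says: "This final visit will take place 14 days after the subject's last dose of YKP3089". The flowchart in SAP Appendix 1 ends at Visit 15 and marks follow-up calls only at Visits 2 to 9. Section 9.2 allows unscheduled visits or calls during the study if the subject or investigator thinks one is needed.

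**The instruction.** Under Post-study Adverse Events (Protocol section 10.1), the subject is told at the last scheduled visit to "report any subsequent event(s) that the subject, or the subject's personal physician, believes might reasonably be related to participation in this study". The investigator's duty to notify the sponsor of later deaths and AEs is limited in the same way, to those occurring "after a subject has discontinued or terminated study participation that may reasonably be related to this study".

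**What continues.** The same text has unresolved AEs followed to resolution, loss to follow-up or another explanation. Section 10.3 has ongoing SAEs followed to their outcome.

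**The analysis.** SAP section 13.1 ends the treatment-emergent period at last dose + 14 days and puts only treatment-emergent events in summary tables. Deaths and non-treatment-emergent SAEs are listed.

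**The concern.** The plan gives SAEs a longer window than other AEs, and Visit 15 serves only the shorter one. For the added days the plan relies on subjects coming forward, and at Visit 15 it tells them to do so only if they or their physician suspect a link to the study. A relatedness limit is ordinary once the reporting period is over. Here it starts at Visit 15, inside the period when every SAE is reportable.

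This is a long-term safety study, and serious events and deaths are what it most needs to capture. A subject admitted for seizures may put this down to the epilepsy and not call. A subject who dies cannot call. The filter also puts the subject's or personal physician's view of causality ahead of the investigator's, because an event that is not volunteered never reaches the investigator for assessment.

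**Working it through.** The plan gives no figure for this gap, so there is none to reproduce. The check compares the stated periods and then puts a rough size on the result.

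**Inputs**
- SAE reporting period: 30 days after the last dose (Protocol 10.1.4).
- Last scheduled contact: day 14 after the last dose (Protocol 9.1.15).
- Later scheduled contact: none found in Protocol 9.1.14 to 9.1.16 or in SAP Appendix 1.

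**Step 1: length of the gap**
- SAE period − day of last contact = 30 − 14 = 16 days.
- 16 / 30 = 0.533, or 53% of the SAE period.

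**Step 2: duty against collection**

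| Days after last dose | SAEs to be reported | How a new SAE comes to light |
|---|---|---|
| up to 14 | all, whatever the cause | Visit 15, where AEs are recorded |
| 15 to 30 | all, whatever the cause | subject, if thought related by subject or personal physician; otherwise by chance or an unscheduled contact |
| after 30 | only if possibly related | same relatedness-limited instruction |

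Duty and instruction agree in the last row. They conflict in the middle row.

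**Step 3: person-time**
Per 1,000 subjects who stop treatment: 1,000 × 16 / 365.25 = 43.8 person-years. The 1,000 is a convenient denominator, not a forecast of how many subjects will stop.

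**Step 4: events, on assumed rates**
The documents give no SAE rate after stopping and no rate of volunteering, so both are assumptions.
- Expected SAEs in the gap = rate × 43.8. At 0.05, 0.10 and 0.20 per person-year: 2.2, 4.4 and 8.8 per 1,000 subjects.
- Missed SAEs = expected × (1 − share volunteered), with the share taken as 30% to 90%.
- Lowest: 2.19 × (1 − 0.9) = 0.2. Highest: 8.76 × (1 − 0.3) = 6.1.

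**Step 5: which outputs are reached**
A new SAE with onset on days 15 to 30 lies beyond last dose + 14 days. It enters no SAP incidence, severity or relatedness table. It belongs in the all-AE listing and the listing of non-treatment-emergent SAEs and, if fatal, the death listing. It is also input to the sponsor's expedited reporting under Protocol 10.3.3.

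**The case against.** The strongest reply is that the formal duty is intact. A site that learns of any SAE by day 30 must report it, and a reaction still present at Visit 15 is followed as an unresolved AE. The threshold in the instruction is also low: the belief of either the subject or the physician is enough. Many people would connect worse seizures after stopping study drug, or trouble from falling phenytoin or phenobarbital levels, with the study. The documents do not show that such risks concentrate in days 15 to 30, and any taper precedes the last dose. All of this stands. It narrows the gap to new events that nobody volunteers, but it does not remove the conflict between duty and instruction.

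Four stronger readings are tempting, and the documents do not support them.
- A reader might infer that the subject's own report is the sole route left. Follow-up of unresolved AEs, the site's own duty and unscheduled contacts all remain.
- A reader might apply the tolerance "Visit windows of ± 7 days allowed for all other open-label visits" to Visit 15 and infer a gap of up to 23 days. That tolerance is given for open-label visits. Visit 15 is post-treatment, has its own flowchart column and is fixed at 14 days. The SAP analysis window for it opens at last dose + 14 days.
- A reader might infer that the related-event figures would be inflated. SAEs from days 15 to 30 enter no relatedness table, and nothing in the documents measures such a shift.
- A reader might link this to contraception, required "during the entire study and for 30 days after the last dose of study medication", and infer a missed pregnancy follow-up. That rule sets no data-collection window, and pregnancy is not in the protocol's SAE definition.

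**Conclusion.** The point holds in a limited form. For a nominal 16 of the 30 SAE days, collection of new events is passive, and the subject instruction conflicts with the all-cause duty. It applies to each subject who stops study drug and attends on day 14. For subjects who do not taper, section 9.1.14 times Visit 15 two weeks from the termination visit, so their gap may be shorter.

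The likely number of lost events is small: about 0.2 to 6.1 SAEs per 1,000 subjects stopping, on assumed rates. The 53% is a share of days, not of events. Under-collection is inferred from the wording and has not been measured. A reader might infer that the study's SAE incidence will be understated. It will not be on this account, because those tables stop at last dose + 14 days. What is weakened is the completeness of the listings of deaths and non-treatment-emergent SAEs, and what reaches the sponsor for expedited reporting.

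The conclusion assumes that no later contact is set out in Protocol Table 1, the rest of section 9.3 or Table 12, which were not fully readable in the text available. The flowchart was read from SAP Appendix 1, which reproduces Amendment 4. Amendment 5 lists only version, date and address changes. The correction should be made, but the point does not threaten the study's main safety summaries.

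**What to change.** 1. Reword the instruction under Post-study Adverse Events. Through 30 days after the last dose, subjects should report any serious event or hospital admission, whatever the cause. The relatedness limit, including the one on the investigator's duty beside it, should apply only after day 30.
2. Add one telephone contact at or shortly after day 30 to section 9.1.15 and the flowchart, asking about any SAE or death regardless of cause. Sites already call subjects between visits early in the study, and being reachable by telephone is an inclusion criterion.

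The first change costs almost nothing and removes the conflict, but on its own it leaves collection passive. The second closes the 16 days for every subject reached. It costs one short call per subject who stops treatment, and some subjects will be unreachable. No added visit, sample or staff is needed, and the SAP tables do not change.

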10.2 Adverse Event Recording and Assessing

All AEs occurring during this clinical trial will be recorded. The investigator will review each event and assess its relationship to drug treatment (unrelated, remote, possible, probable, or definite). Each sign or symptom reported will be graded on a 3-point severity scale (mild, moderate, or severe), and the date of onset, time of onset, and outcome of each event will be noted.

The relationship of each AE to study drug will be assessed using the following definitions:

Definite	
 • Distinct temporal relationship with drug treatment • Known reaction to agent or chemical group, or predicted by known pharmacology • Event cannot be explained by subject's clinical state or other factors
Probable	
 • Reasonable temporal relationship with drug treatment • Likely to be known reaction to agent or chemical group, or predicted by known pharmacology • Event cannot easily be explained by subject's clinical state or other factors
Possible	
 • Reasonable temporal relationship with drug treatment • Event could be explained by subject's clinical state or other factors
Remote	
 • Poor temporal relationship with drug treatment • Event easily explained by subject's clinical state or other factors
Unrelated	
 • Event occurring before dosing • Event or intercurrent illness due wholly to factors other than drug treatment

The following definitions for rating severity will be used:

- *Mild*: The AE is easily tolerated and does not interfere with daily activity.
- *Moderate*: The AE interferes with daily activity, but the subject is still able to function.
- *Severe*: The AE is incapacitating and requires medical intervention.

